6.7.6 Clinical Significance

Changes in unblinded laboratory values, vital signs or other diagnostic procedure outcomes/results are only considered to be AEs if they are judged to be clinically significant (ie, if some intervention or therapy is required or if the investigator judges the change to be beyond the expected variation). Any abnormalities will automatically be considered clinically significant unless the investigator indicates not clinically significant directly on the laboratory paperwork or source documentation.

6.7.7 Serious Adverse Events

6.7.7.1 Definition

An SAE is defined by the investigator or sponsor as any AE occurring during an investigational study that result in any of the following outcomes:

- Death
- Life-threatening AE
- Hospitalization or prolongation of existing hospitalization
- A persistent or significant disability (substantial disruption of the ability to conduct normal life functions)/incapacity

- A congenital anomaly/birth defect
- Important medical events that may not result in death, may be life threatening, or may require hospitalization may be considered an SAE when, based upon appropriate medical judgment, they may jeopardize the subject and may require medical or surgical intervention to prevent one of the outcomes listed in this definition. Examples of such medical events include allergic bronchospasm requiring intensive treatment in an emergency room or at home, blood dyscrasias or convulsions that do not result in subject hospitalization, or the development of drug dependency or drug abuse.

Research subjects will be instructed to notify the research center for any emergent condition and will be given the emergency contact number for the study during the consenting process.

6.7.7.2 Expectedness

SAEs must be assessed as to whether they were expected to occur or unexpected, meaning not anticipated based on current knowledge about the investigational compound found in the protocol or Investigator Brochure (IB) for Rayaldee (CTAP101 Capsules). Categories are:

- Unexpected nature or severity of the event is not consistent with the product information;
- **Expected** event is known based on the product information.

6.7.7.3 Reporting Serious Adverse Events

Any AE considered serious by the investigator that meets the previously mentioned criteria must be reported to OPKO Pharmacovigilance at the following number within 24 hours from the time when site personnel first learn about the event.

SAFETY REPORTING Contact: OPKO Pharmacovigilance

Fax:

E-mail:

The IRB/IEC should be made aware according to currently prescribed institutional guidelines. A written report should be provided consisting of the SAE Form and other necessary source documents. If the subject is hospitalized because of or during the course of an SAE, then the investigator should attempt to obtain a copy of the hospital discharge summary and any pertinent laboratory or diagnostic reports, and provide them to the sponsor or designee as soon as possible.

For any information not available at the time of the first report that becomes available later, the investigator should update the SAE Form and eCRFs and provide any additional documentation to OPKO Pharmacovigilance and IRB/IEC within 1 working day of receipt.

The sponsor or designee will notify the appropriate regulatory agencies of any serious and unexpected SAEs associated with the use of the investigational study drug according to regulations. Copies of any reports to regulatory agencies regarding serious and unexpected SAEs will be provided to the investigators by the sponsor or designee for review and submission to the DSMB and IRB/EC.

If using a local IRB/EC, the investigator is responsible for informing his or her IRB/EC per its requirements of any SAEs at that site. Copies of SAE correspondence with the IRB/EC, regulatory authorities, and other physicians must be provided to the Study Contact.

Protocol CTAP101-CL-2014	
CTAP101 (calcifediol) Extended-release Ca	psules

A subject experiencing one or more SAEs will receive treatment and FU evaluations by the investigator, or they will be referred to another appropriate physician for treatment and FU.

All SAEs will be followed to at least Day 42 or until resolution. Should the event become indistinguishable from the chronic disease condition, the subject will be followed for 14 days after the last investigational study drug administration and subsequently all events will be closed.

6.7.8 Treatment-Emergent Adverse Events

A TEAE is defined as any AE with onset or worsening reported by a subject from the time that the first dose of study drug is taken in this study until 14 days following discontinuation of study drug administration.

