3.5 Study Duration

The study is expected to be completed within approximately 8-12 weeks from the time of initial subject enrollment (first subject consented) to study completion for the last subject (last subject out/last visit complete). Each enrolled subject will participate in the study after randomization for up to 42 days (Day 1 through Day 42).

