5.3 Treatments Administered

5.3.1 **Dosing Instructions**

Study drug should **NOT** be administered to individuals known to be allergic to any component of the drug.

Subjects will be instructed to take a loading dose of 10 capsules (300 mcg) of study drug per day on Days 1, 2 and 3 at bedtime after fasting for at least 3 hours following dinner, with any nonalcoholic liquid, by the oral route. On Days 4-27, subjects will take a maintenance dose of 2 capsules per day at bedtime unless otherwise directed. Patients should remain fasted for at least 3 hours after administration of study drug.

Study drug will be provided in containers labeled as investigational study drug as per the Packaging and Labeling below in Section 5.9. The interactive response technology (IRT) will dispense an appropriate bottle configuration to each patient per the dosing requirements. Each bottle will contain either active drug or a matching placebo.

Drug accountability will be performed at each visit until the end of the 28-day treatment period. All procedures being performed during the course of this clinical study are listed sequentially by visit in Section 7: Study Activities, and may be found as a table in APPENDIX 1: Schedule of Events.

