6.7.3 AE Collection Period

Adverse events which are determined as non-serious events that occur after the ICF has been signed and after the initiation of study drug will be documented in the source document and followed to a satisfactory resolution, until the investigator deems the event to be chronic or the subject to be stable, or until the subject's participation in the study ends. Adverse events that occur after the ICF has been signed but prior to the initiation of study drug will be captured as medical history. Serious adverse events that occur after the ICF has been signed must be reported to the sponsor (as per protocol Section 6.7.7.3) and will be documented in the source document and followed to a satisfactory resolution, until the investigator deems the event to be chronic or the subject to be stable, or until the subject's participation in the study ends.

New or changes in COVID-19 symptoms are expected over the course of the COVID-19 infection and should not be reported as AEs unless intervention was required or in the opinion of the investigator they are considered clinically significant. All COVID-19 SAEs should be reported regardless.

Information to be collected includes description of the event (event term), date of onset, date of resolution, investigator-specified assessment of severity and relationship to the investigational study drug, seriousness, action taken with study drug (if applicable), as well as any required treatment or evaluations and outcome.

AEs resulting from concurrent illnesses, reactions to concurrent illnesses, reactions to concurrent medications, or progression of disease states must be documented as AEs. Pre-existing conditions (present before the start of the AE collection period) are considered concurrent medical conditions and should NOT be recorded as AEs, but must be documented in the medical history section of the eCRF and in the source document. However, if the subject experiences a clinically significant worsening or complication of such a concurrent condition (eg, pneumonia),

Protocol CTAP101-CI	-2014	
CTAP101 (calcifediol)	Extended-release Ca	psules

the worsening or complication should be recorded as an AE. Investigators should ensure that the AE term recorded captures the change in the condition.

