6.9 Removal of Subjects from the Study or Study Drug / Stopping Criteria

The investigator may discontinue a subject from study drug treatment for any of the following reasons:

- A major protocol deviation occurs;
- A serious or intolerable AE occurs;
- The subject has a confirmed pregnancy;
- A clinically significant change in a laboratory parameter occurs (eg, increase in serum calcium above upper limit allowed); and,
- A clinically significant change in ECG at Visit 3 occurs as compared to baseline (eg, prolongation of QT interval).

The investigator may withdraw a subject from the study for any of the following reasons:

- The subject requests to be discontinued from the study (withdraws consent); or,
- The subject is lost to follow-up.

Subjects who develop severe (CTCAE \geq 3) abnormalities (low or high) of serum phosphorus, uric acid or plasma iPTH will be withdrawn from study drug treatment.

Enrollment of subjects into the study will be paused if mortality in the treatment arm is $\geq 7\%$ higher compared to the placebo arm until the DSMB makes an assessment about causality, and may resume once the DSMB deems it acceptable to continue (if applicable).

No subject replacement is planned. All subjects withdrawn from treatment will continue in the study until study completion and perform all assessments unless consent is withdrawn. The investigator will be requested to make all reasonable efforts to obtain clinical status at FU.

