12.3 Pharmacokinetics

Absorption

No food effect study was conducted with 30 mcg and 60 mcg doses of RAYALDEE. However, a food effect study with a supratherapeutic dose of 450 mcg in healthy subjects showed an approximately 5-fold increase in maximum serum calcifediol concentration (C_{max}) and a 3.5-fold increase in AUC_{0-t} when RAYALDEE was administered with a high fat, high calorie meal compared to fasting.

Exposure to calcifediol increased proportionally over the dose range of 30 to 90 mcg following repeated daily administration of RAYALDEE at bedtime to subjects with secondary hyperparathyroidism, chronic kidney disease and vitamin D insufficiency. Steady-state levels of serum total 25-hydroxyvitamin D are reached after approximately 3 months [see Clinical Studies (14)].

Distribution

Calcifediol is extensively bound to plasma proteins (>98%). The mean apparent volume of distribution is 8.8 L in healthy subjects following a single oral dose of RAYALDEE, and 30.1 L in subjects with stage 3 or 4 chronic kidney disease following repeated dosing.

Elimination

The mean elimination half-life of calcifediol is approximately 11 days in healthy individuals following a single dose of RAYALDEE, and approximately 25 days in patients with stage 3 or stage 4 chronic kidney disease following repeated once daily dosing.

Metabolism

Production of calcitriol from calcifediol is catalyzed by the 1-alpha-hydroxylase enzyme, CYP27B1, located in the kidney and other tissues. CYP24A1, located in all vitamin D-responsive tissues, catabolizes both calcifediol and calcitriol to inactive metabolites.

Excretion

Excretion of calcifediol occurs primarily through the biliary fecal route.

Specific Populations

Age, Gender and Race

Based on a population pharmacokinetic analysis, age, gender and race had no meaningful impact on steady-state concentrations of calcifediol following RAYALDEE administration.

Hepatic Impairment

The pharmacokinetics of RAYALDEE have not been investigated in patients with hepatic impairment.

Renal Impairment

Based on the population pharmacokinetics analysis, there was no meaningful difference in calcifediol steady-state concentrations following repeated RAYALDEE administration in patients with stage 3 or stage 4 chronic kidney disease.

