6.9.1 Adverse Events

All AEs will be collected on the eCRF and coded via system organ class (SOC) and preferred term using MedDRA version 23.0 or higher. Additionally, the intensity of all AEs will be coded using CTCAE v. 5.0. Detailed information collected for each TEAE will include: AE number, a description of the event, start date, end date or ongoing as of date, outcome, therapy for event, whether the AE is serious, seriousness criteria (life-threatening, death, hospitalization/prolongation of hospitalization, congenital anomaly, persistent or significant disability/incapacity, required intervention to prevent permanent impairment/ damage), severity, and relationship to the study drug. The incidence of the AEs will be summarized by treatment group for all TEAEs, potentially drug-related TEAEs, serious TEAEs, discontinuation due to TEAEs, TEAEs by relationship to study drug (definite, probable, possible, unrelated) and TEAEs by severity (mild, moderate, severe). The number and percentages of subjects with a TEAE will be summarized by SOC and preferred term and presented overall and by treatment group. TEAEs will be sorted in descending order of total incidence of SOC and preferred term within each SOC. The percentages will be based on the number of Safety subjects in a particular treatment group. If a subject has more than one TEAE that code to the same preferred term, the subject will be counted only once for that preferred term. Similarly, if a subject has more than one TEAE within a SOC category, the subject will be counted only once in that SOC category. All AEs collected on the eCRF will be included in the listings. An additional listing of all subject deaths will also be provided.

Diagnostic procedures will be collected separately in the eCRF and coded via SOC and preferred term using MedDRA version 23.0 or higher in a manner similar to AEs.

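### Adverse events arising more than 14 days after study drug stops reach only the listings, although subjects withdrawn from drug are followed to Day 42

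*Protocol*

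**What the plan says.** Protocol 6.7.8 starts the treatment-emergent window at the first dose and runs it "until 14 days following discontinuation of study drug administration". The SAP uses the term throughout but sets no window of its own, so the protocol definition governs.

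Stopping drug does not end follow-up. Protocol 6.9 states: "All subjects withdrawn from treatment will continue in the study until study completion and perform all assessments unless consent is withdrawn". Protocol 3.5 has subjects taking part "for up to 42 days (Day 1 through Day 42"). AEs are assessed at each visit, including the Day 42 telephone visit (Protocol 7.11 and Appendix 1). Protocol 6.7.3 has recorded events followed until they resolve or stabilise, "or until the subject's participation in the study ends".

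The reporting is narrower. SAP 6.9.1 says: "The incidence of the AEs will be summarized by treatment group for all TEAEs", and each further AE summary in that section is likewise a TEAE summary. In SAP 8.1, Tables 14.3.1.1 to 14.3.1.12 are all titled as TEAE tables; 14.3.1.3 is the serious-event table. AEs outside the window go to the by-subject listings, with a separate listing of deaths.

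**The concern.** The trial keeps subjects under observation after they stop drug, then leaves part of that observation out of every planned comparison of AEs by arm. The cut-off is set by each subject's own stopping date, which comes after randomisation. Two subjects with the same event on Day 30 are treated differently: it is tabulated for the one who completed treatment and only listed for the one who stopped on Day 10.

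The rule bears on the subjects whose later course is of most interest for safety. Protocol 6.9 allows drug to be stopped for a serious or intolerable AE or for a clinically significant laboratory or ECG change, and it withdraws from drug those with severe phosphorus, uric acid or iPTH abnormalities. A new or worsening event in such a subject after stop day + 14 enters no incidence table. A late hospitalisation could count towards the 42-day efficacy endpoint and still be missing from the serious-TEAE table.

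**Working it through.** The plan states no figure to reproduce here; the check is a timeline and a decay calculation.

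**Inputs**
- Window end: 14 days after drug stops (Protocol 6.7.8).
- End of participation: Day 42 (Protocol 3.5; Visit 6 is Day 42 ± 4).
- Last scheduled dose: Day 27 (Protocol 5.3.1: "On Days 4-27, subjects will take a maintenance dose of 2 capsules per day at bedtime unless otherwise directed").
- Calcifediol half-life (Protocol Appendix 2, section 12.3): about 11 days in healthy individuals after a single dose, and "approximately 25 days in patients with stage 3 or stage 4 chronic kidney disease following repeated once daily dosing". Protocol 3.2 allows stage 3-4 CKD patients to enrol.

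**Days outside the window.** Taking discontinuation as the day of the last dose, window end = last dose day + 14, and days outside = 42 − window end.

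| Last dose | Window closes | Days outside, to Day 42 | Share of 42 days |
|---|---|---|---|
| Day 3 | Day 17 | 25 | 60% |
| Day 7 | Day 21 | 21 | 50% |
| Day 10 | Day 24 | 18 | 43% |
| Day 14 | Day 28 | 14 | 33% |
| Day 20 | Day 34 | 8 | 19% |
| Day 27 (completer) | Day 41 | 1 | 2% |

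If Visit 6 falls on Day 46, a completer has 46 − 41 = 5 days outside. If discontinuation is dated to the day after the last dose, each window closes one day later. The protocol does not say whether a temporary suspension for calcium counts as discontinuation.

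**Drug-raised 25D remaining.** Under first-order decay, the fraction remaining t days after the last dose is 0.5^(t / half-life).
- At window closure (t = 14): 0.5^(14/11) = 0.41 and 0.5^(14/25) = 0.68.
- At Day 42 after a last dose on Day 10 (t = 32): 0.5^(32/11) = 0.13 and 0.5^(32/25) = 0.41.

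**SAE follow-up in Protocol 6.7.7.3.** The paragraph begins: "All SAEs will be followed to at least Day 42 or until resolution". It then provides that, if the event can no longer be told apart from the chronic disease, follow-up lasts 14 days after the last dose and events are then closed. With a last dose on Day 10, the first statement gives at least Day 42 (unless the event resolves) and the second gives Day 24.

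**The case against.** The strongest reply is that little is lost. All AEs are listed and deaths have their own listing. Hypercalcemia and hyperphosphatemia are compared between arms and tabulated overall and by visit in the Safety population, with no stated TEAE limit (SAP 6.9.5, Table 14.4.4.3). Chemistry, hematology, ECG and vital signs are tabulated by visit. Emergency or urgent care visits, low oxygen saturation, hospitalisation, ventilation and death are counted over 42 days (SAP 5.3). The event that causes drug to be stopped starts inside the window and is tabulated. For completers the 14-day rule almost matches planned follow-up, and SAP 8.1 says its table list is not exhaustive. All of this stands and limits the size of the point. It does not supply an AE incidence table by arm for the whole follow-up, and none is named.

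The half-life argument also has limits. The 25-day figure comes from repeated dosing, so it may not fit a subject who took only the loading dose. Nor is persistence shown to be a hazard: on Protocol 3.2's figures (baseline about 25 ng/mL, loading rise of 20 to 35), 25 + 0.41 × 20 = 33 and 25 + 0.68 × 35 = 49 ng/mL, inside the 30 to 100 reference range in Protocol 1.1. It shows that exposure continues past day 14, not that harm does.

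Three stronger readings are tempting but unsupported.
- A reader might infer that faster resolution on active drug shortens that arm's windows. SAP 4.4 speaks of resolved subjects leaving the study early, not of stopping drug under continued follow-up, and Protocol 6.9 does not list resolution as a reason to stop drug.
- A reader might infer from the subgroup treated for 10 days or fewer that many early stoppers are expected. No number is given, and subjects who leave the study would also fall in that subgroup.
- A reader might infer that AE collection itself is cut short. It continues to Visit 6 for all who remain; only the tabulation stops.

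**Conclusion.** The point holds as a gap in tabulation. For subjects who stop drug early and stay in follow-up, AEs with onset or worsening after stop day + 14 enter no named AE incidence table, serious events included. The excluded span is 25 of 42 days for a last dose on Day 3 and 18 days for Day 10; completers are almost unaffected. When the window closes, 41% to 68% of the drug-raised 25D would remain, given first-order decay and the package insert half-lives.

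The number of early stoppers is not stated, so the count of omitted events cannot be computed. The documents also do not show that the omission favours one arm. What can be said is that the safety comparison uses a cut-off that depends on a post-randomisation event when a common one is available. This does not touch the primary efficacy analyses. It is worth correcting because the correction is cheap and uses data the trial already collects.

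**What to change.** In the SAP, tabulate all AEs and all serious AEs by arm in the Safety population from first dose to the end of participation (Visit 6 or last contact), whenever drug was stopped. Either extend the TEAE definition to that period and apply it to all 14.3.1.x tables, or add these tables beside the 14-day version. If the 14-day version is kept, state how the discontinuation date is set and whether a temporary suspension counts.

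The cost is one definition or a small set of extra tables, with no new data and no change to visits. The downside is that some events remote from dosing will be counted, under the same rule in both arms.

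Separately, the two SAE follow-up statements in Protocol 6.7.7.3 (to at least Day 42 or resolution; 14 days after the last dose) should be reconciled, so that sites know which governs when drug stops early.

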6.8 Concomitant Medication Assessments

The study coordinator or designee will record concomitant medication history (previous three months) in the source document and eCRF.

6.9 Removal of Subjects from the Study or Study Drug / Stopping Criteria

The investigator may discontinue a subject from study drug treatment for any of the following reasons:

- A major protocol deviation occurs;
- A serious or intolerable AE occurs;
- The subject has a confirmed pregnancy;
- A clinically significant change in a laboratory parameter occurs (eg, increase in serum calcium above upper limit allowed); and,
- A clinically significant change in ECG at Visit 3 occurs as compared to baseline (eg, prolongation of QT interval).

The investigator may withdraw a subject from the study for any of the following reasons:

- The subject requests to be discontinued from the study (withdraws consent); or,
- The subject is lost to follow-up.

Subjects who develop severe (CTCAE \geq 3) abnormalities (low or high) of serum phosphorus, uric acid or plasma iPTH will be withdrawn from study drug treatment.

Enrollment of subjects into the study will be paused if mortality in the treatment arm is $\geq 7\%$ higher compared to the placebo arm until the DSMB makes an assessment about causality, and may resume once the DSMB deems it acceptable to continue (if applicable).

No subject replacement is planned. All subjects withdrawn from treatment will continue in the study until study completion and perform all assessments unless consent is withdrawn. The investigator will be requested to make all reasonable efforts to obtain clinical status at FU.

